3.3.1 Overview of Study Procedures

Table 6 displays an overview about the study procedures at the different visits which are described in detail afterwards.

Table 6: Procedures by Visit Type

Procedures	Enrollment	Implant	QP ExCELS and MPP sub-study Follow-up	Interim Follow-up [†]
Informed consent	x			
Verification of inclusion and exclusion criteria	x			
Demographic data and comorbidities	x			
NYHA class and heart failure symptoms	x*		x	x
ECG and ECHO values (if performed routinely)	x			
Co-morbidities	x			
Cardiovascular medication	x			
CRT-D implantation		x		
Implantation information		x		
Programming of device settings		x	x	x
Standard device evaluation		x	x	x
Adverse event reporting	x	x	x	x
Completion of eCRFs	x	x	x	x

[†] Interim follow-ups may be collected when related to an AE, system revision or for a heart failure hospitalization for enrolment into the MPP sub-study. Implant information only needs to be collected if a system revision has occurred.

* NYHA collected within 30 days prior to implant if enrolled after implantation.

3.3.2 QP ExCELS Enrollment

Prior to enrollment, the physician selects potential candidates which are eligible for the clinical study. If the potential subject meets all inclusion and exclusion criteria (Sections 3.1.3 and 3.1.4), the potential subject is asked to read and sign an Informed Consent Form. The potential subject should be provided with sufficient time to consider participation in the trial.

Subjects are 'provisionally enrolled' into the MPP sub-study upon signing the Informed Consent Form and meeting the inclusion/exclusion criteria at time of consent. All subjects enrolled in the study must be entered in the subject enrollment log. The consent process should be documented within the subject's medical record.

After informed consent has been obtained, the following data should be collected for baseline evaluation:

1. Demographic characteristics (year of birth, gender, height, weight)
2. Device therapy indication
3. ECG diagnosis, if routinely performed
4. NYHA class
 - a) For subjects enrolled prior to implant, current NYHA class as assessed by study personnel at the time of enrollment
or
 - b) NYHA class obtained within 30 days prior to implant for subjects enrolled after implant.
5. Most recent LVEF, obtained prior to implant
6. Comorbidities and cardiac medications

The Enrollment eCRF needs to be completed using the data collected during the enrollment visit.

3.3.3 Implantation

Implantation may occur after enrollment of the subject or may occur prior to enrollment if an NYHA assessment within 30 days prior to the implant date is available in the subject's medical record. For subjects implanted prior to enrollment, implant details and device data will be collected retrospectively.

At implantation, the following data is collected:

1. Implanted devices (manufacturer, model, serial number), plus date of implant
2. Implantation site, and if available, implant approach
3. Sentus QP lead implant success
5. Activation of the recommended device settings as listed in Section 3.2.3
6. Sentus QP lead evaluation from implant procedure:

- Determine LV lead impedance
 - Determine LV mean R-wave sensing amplitudes
 - Determine LV pacing threshold at 0.4 ms pulse width for the pacing vector programmed at the end of implantation
7. Device programming and settings at end of implantation procedure
 8. Store the electronic procedure data (including final device settings, measurements, episodes) from the BIOTRONIK programmer
 9. Complete the Implantation eCRF using data collected during implant and information from the end of procedure device evaluation
 10. Document any reportable adverse event (e.g. phrenic nerve stimulation, high LV pacing threshold, etc.) during the procedure on the respective eCRF.

Please note:

1. If the BIOTRONIK Ilivia 7 or Acticor/Rivacor HF-T QP family CRT-D and/or Sentus QP LV lead were not implanted, the subject will be exited from the clinical investigation using a Study Termination eCRF.
2. In order to support the CRT responder assessment for enrollment into the MPP sub-study, the MPP feature should not be programmed ON prior to the MPP sub-study enrollment.

3.3.4 QP ExCELS 6-month Follow-up

Six (6) months (\pm 45 days) after implantation, subjects return to the investigational site for an in-office assessment of their implanted system. To support CRT Responder Assessment at 6-months post-implant, QP ExCELS 6-month follow-ups occurring prior to the visit window or more than 30 days after the visit window will not be allowed.

The following data should be collected:

1. Perform device interrogation:
 - Determine LV lead impedance
 - Determine LV lead R-wave sensing amplitude
 - Determine the LV pacing threshold at 0.4 ms pulse width for the programmed pacing vector
 - Determine LV pacing threshold @ any pulse width (allowing for a minimum 2.5 V safety margin) and document occurrence of phrenic nerve stimulation for additional LV pacing vectors.
2. Obtain NYHA classification and HF hospitalization status to determine CRT Responder Assessment classification

3. Screen subject for MPP sub-study by confirming subject meets all of the MPP sub-study specific inclusion criteria and none of the MPP sub-study specific exclusion criteria (Sections 3.1.3 and 3.1.4). If the subject qualifies for the MPP sub-study, complete MPP sub-study enrollment procedures in Section 3.3.5.
4. Device programming and settings at end of follow-up.
5. Store the electronic procedure data (including final device settings, measurements, episodes) of the BIOTRONIK programmer on an appropriate USB flash drive.
6. Complete the appropriate Follow-Up eCRF.
7. Document any reportable adverse event (e.g. phrenic nerve stimulation, high LV pacing threshold, etc.) using the respective eCRF.

If subject does not qualify for the MPP sub-study, no further follow-up visits are required. A study termination eCRF is not required.

3.3.5 MPP Sub-Study Enrollment

MPP sub-study enrollment occurs after a subject has been screened and determined to meet all MPP sub-study specific inclusion criteria and none of the exclusion criteria. QP ExCELS subjects with a heart failure hospitalization will be considered to have a CRT Responder Assessment classification of worsened and are eligible for the MPP sub-study. Subjects with a heart failure hospitalization occurring prior to the 6 month post-implant follow-up visit may be enrolled between 3 and 6 months post-implant by completing an interim follow-up eCRF (Section 3.3.8.1) or be enrolled at the QP ExCELS 6 month follow-up visit (Section 3.3.4).

MPP optimization may be performed or not performed per investigator discretion at the time of enrollment into the MPP sub-study. The investigator will determine if MPP optimization will be performed for each subject and which method will be used (e.g. QRS width, electrical delay, echocardiography, etc.). MPP programmed parameters may be adjusted as needed during the follow-up period for MPP sub-study subjects.

After a patient has been screened and determined to be eligible for the MPP sub-study, the following data will be collected:

1. Turn MPP ON and collect MPP programmed settings
2. Document MPP optimization method
3. Obtain Patient Global Assessment
4. Document any reportable Adverse Events
5. Review and complete the appropriate eCRFs

The MPP feature must be programmed ON from MPP enrollment until the subject exits the sub-study. Subjects who have the MPP feature permanently turned OFF prior to completion of the sub-study will be required to report a protocol violation.

3.3.6 3-Month MPP Follow-up

At a 3-month MPP follow-up (90 ± 30 days post-MPP enrollment), subjects return to the investigational site for an in-office assessment of their heart failure status and implanted system.

The following data should be collected:

1. Collect MPP programmed settings
2. Obtain NYHA classification and HF hospitalization status
3. Obtain Patient Global Assessment
4. Collect device initial and final programmed settings
5. Document any reportable Adverse Events
6. Review and complete the appropriate eCRFs

3.3.7 6-Month MPP Follow-up

At the 6-month follow-up (180 ± 30 days post-MPP enrollment), subjects return to the investigational site for an in-office assessment of their heart failure status and implanted system.

1. Collect MPP programmed settings
2. Obtain NYHA classification and HF hospitalization status
3. Obtain Patient Global Assessment
4. Collect device initial and final programmed settings
5. Document any reportable Adverse Events
6. Review and complete the appropriate eCRFs
7. Complete a study termination eCRF documenting MPP sub-study completion

Following the 6-month MPP follow-up, all subjects may be programmed to MPP or standard BiV pacing, per physician discretion.

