The purpose of Secondary Endpoint 2 is to evaluate a modified CCS, determining a responder classification based on changes in NYHA class, Patient Global Assessment (PGA), HF hospitalization, and cardiovascular death, where the PGA will ask subjects to assess how their overall status has changed since prior to receiving CRT therapy (markedly better, better, unchanged, worse, markedly worse).

Modified Responder Classification (CCS + PGA) at the 6-Month MPP Follow-Up (evaluated compared to MPP enrollment visit):

- “Improved”:
 - No HF hospitalization or cardiovascular death, AND
 - Neither NYHA class is worsened or PGA is worsened (“worse” or “markedly worse”), AND
 - NYHA class is improved or PGA is improved (“better” or “markedly better”)
- “Unchanged”:
 - No HF hospitalization or cardiovascular death, AND
 - NYHA class is unchanged, AND
 - PGA is unchanged (“unchanged”)
- “Worsened”:
 - HF hospitalization or cardiovascular death has occurred, OR
 - NYHA class is worsened or PGA is worsened (“worse” or “markedly worse”)

2.1.4 Secondary Endpoint 3

The purpose of Secondary Endpoint 3 is to evaluate the Responder Classification (as defined in Section 2.1.1) in which both “Improved” and “Unchanged” subjects will be classified as responders. At the time of enrollment into the MPP sub-study, MPP sub-study subjects have already been found to have no change or worsening in their HF status with BiV pacing. Since HF is a chronic and progressive condition,

these subjects may be expected to continue to worsen during the MPP follow-up period or remain stable with careful management. In this secondary endpoint, a status of “Unchanged” (in addition to “Improved”) during the MPP follow-up period will be considered a responder to MPP.

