2.6.1 Replacement of Missing Data

The last observation carried forward (LOCF) principle will be utilized for the analysis of NYHA Classification and Patient Global Assessment for primary endpoint 1 and secondary endpoints 2 and 3.

Missing NYHA and patient global assessment data at either the enrollment or follow-up visits affects the number of subjects that can be included in the analysis. It is possible that subjects or study personnel may either forget or choose not to answer one or more of the questions related to NYHA classification or patient global assessment.

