3.2.6 Patient Global Assessment (PGA)

During the course of the MPP sub-study a PGA will be given to assess how the subject's overall status has changed since prior to receiving CRT therapy (markedly better, better, unchanged, worse, markedly worse). It is important to minimize the influence on the respondent by limiting their interaction and verbal exchanges with spouses or other individuals who may affect results while the assessment form is being completed.

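### Section 3.3.5 lists the enrollment PGA after MPP is switched on and does not require it to be completed first, so the only possible pre-MPP PGA may be taken with MPP already active

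*Combined protocol and SAP*

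**What the plan says.** Section 3.3.5 introduces its list with "After a patient has been screened and determined to be eligible for the MPP sub-study, the following data will be collected". Item 1 is "Turn MPP ON and collect MPP programmed settings", item 2 is "Document MPP optimization method" and item 3 is "Obtain Patient Global Assessment". The same section leaves optimization to the site: "MPP optimization may be performed or not performed per investigator discretion at the time of enrollment into the MPP sub-study".

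Section 2.1.3 heads the secondary endpoint 2 classification "evaluated compared to MPP enrollment visit". Section 2.6.1 applies LOCF to NYHA class and the PGA, and adds: "Missing NYHA and patient global assessment data at either the enrollment or follow-up visits affects the number of subjects that can be included". Section 3.2.6 anchors the PGA question to the time before CRT.

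**The concern.** A subject who has just been classed as a non-responder may have the new feature activated, and perhaps optimized, and then be asked to rate overall status. The study is single-arm and the subject knows what has been done. The answer can then pick up expectation or an immediate sensation from the new pacing.

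The protocol guards the BiV-only period elsewhere. Sections 3.2.3 and 3.3.3 say MPP should stay off until sub-study enrollment so that the responder assessment is supported, and Section 3.1.4 excludes subjects who have already received MPP. The enrollment PGA has no such protection. If it is taken after activation, the study has no patient-reported reading on BiV pacing alone, and none can be recovered later. Because the PGA asks about change since before CRT, the enrollment reading is also the only one that could show whether a favourable answer at 6 months was already present on BiV pacing.

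**Working it through.** **1. Is there any other pre-MPP PGA?**

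| Place | NYHA / HF hospitalization | PGA |
|---|---|---|
| 3.3.4, 6-month screening visit | listed | not listed |
| 3.3.8.1, screening after HF hospitalization | listed | not listed |
| Table 6, procedures by visit | NYHA row present | no row |
| 3.3.5, MPP enrollment | already obtained at screening | item 3, after MPP ON |
| 3.3.6 and 3.3.7, MPP follow-ups | listed | listed |

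Section 2.1.5 mentions a PGA at each visit among the additional data, but Section 3.2.6 places the PGA within the MPP sub-study and neither screening list includes it. The Section 3.3.5 PGA is therefore the only candidate. Both screening sections send the subject to Section 3.3.5 only after eligibility is settled, so the NYHA baseline precedes activation.

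**2. Is the order fixed anywhere?** Section 2 says MPP is programmed on after sub-study enrollment. That does not settle the order of steps within the enrollment visit, and no other sentence does. A site working down the list takes the PGA with MPP on.

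**3. How can the enrollment PGA reach secondary endpoint 2?** Under Section 2.1.3 the PGA counts as improved or worsened by its response category. No change from the enrollment PGA is defined. With a 6-month PGA, the enrollment value is not used by the written rules. With only a 3-month PGA, LOCF carries that one. The enrollment PGA is carried only if both later PGAs are missing.

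Take a subject with no later NYHA or PGA and no HF hospitalization or cardiovascular death, and apply LOCF as written. NYHA is carried as unchanged, so the enrollment PGA alone decides the class:

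- better or markedly better: Improved
- unchanged: Unchanged
- worse or markedly worse: Worsened

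**4. How many subjects at most?** Section 2.5 plans a 10% loss: 90/(1 − 0.10) = 100 enrolled, and 100 − 90 = 10 lost. If every loss fell before the 3-month PGA, 10 of 100 enrollment values would be carried. At the enrollment cap of 110, 10% is 11. Losses after the 3-month visit lower this count. The documents give no figure for how many subjects would answer differently because MPP had just been switched on, so no bias in the endpoint can be calculated.

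**5. Is the sample size affected?** The plan's 90 reproduces with the exact one-sided binomial test of 3% against 10%. Success at 7 or more responders of 90 has type I error 0.0188 (below 0.025 and 0.0224) and power 0.8075; n = 89 gives 0.798. The PGA does not enter this calculation.

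**The case against.** The strongest objection is that the list is an inventory, not a sequence. Its lead-in speaks of data to be collected. Sections 3.3.4 and 3.3.8.1 put interrogation and NYHA in opposite orders for the same screening. Sections 3.3.6 and 3.3.7 list the initial device settings after the PGA. Section 3.3.3 lists adverse events during the implant procedure after completion of the eCRF. This stands: a reader might infer that the PGA is always taken after treatment has started, but the documents show only that the order is left open and that the numbering points that way. Nor can one say that MPP has been optimized by then, since optimization is discretionary and item 2 only records the method.

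A reader might also infer that a change-from-enrollment PGA result is biased. The plan defines no such result. Nor does it call the enrollment PGA a BiV baseline; that role is only implied by the heading of secondary endpoint 2 and by Section 2.6.1.

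The same reasoning does not extend to Sections 3.3.6 and 3.3.7. MPP has been on for months by then, and their first item only collects settings.

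The sentence in Section 3.2.6 beginning "It is important to minimize the influence on the respondent" concerns spouses and other individuals, not programming order, so it gives no direct support.

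Finally, reordering cannot remove all expectation, because subjects consent to the sub-study at the outset. It removes only what activation and optimization at that visit add. Section 2.5 also treats the 10 planned losses as non-evaluable, which makes the upper bound generous, although Section 2.6.2 calls for all available data from fully enrolled subjects.

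**Conclusion.** The point holds as a small gap in the visit procedures. The enrollment PGA may be taken after activation, nothing prevents it, and no other PGA could serve as a pre-MPP reading. What can be affected is secondary endpoint 2, through its enrollment-visit heading and through LOCF, and the descriptive PGA data. The carried-forward route covers at most 10 of 100 subjects (11 of 110) and probably fewer. That bound assumes the planned 10% loss, all of it before the 3-month PGA, and that LOCF may start from the enrollment value, which Section 2.6.1 does not rule out. The direction of any bias is unknown. Secondary endpoint 2 has no stated hypothesis or success criterion. The primary endpoint, secondary endpoints 1 and 3 and the sample size are unaffected.

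**What to change.** In Section 3.3.5, make the PGA item 1 and add a sentence saying that it is completed before MPP is programmed on and before any optimization. Sections 3.3.6 and 3.3.7 need no change. The cost is a reordered list and one sentence: same visit, same form, no added procedure. PGAs already collected under the present list could not be corrected.

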3.3.8 Interim Follow-up

Interim follow-ups may occur anytime during the clinical investigation; however, only those interim evaluations in support of MPP sub-study enrollment due to a heart failure hospitalization between 3 and 6 months post-implant and those related to adverse events or system revisions may be collected in the clinical investigation. Interim follow-ups can be visits scheduled by physicians according to clinical routine, visits scheduled by the physician due to BIOTRONIK Home Monitoring[®] alerts or trends, or visits initiated by the subject.

3.3.8.1 MPP Sub-Study Heart Failure Hospitalization

Subjects with a heart failure hospitalization meeting the definition in Section 6.1.4 may be enrolled into the MPP sub-study between 3 and 6 months post-implant by completing an interim visit eCRF. The following procedures are required:

1. Obtain NYHA classification and HF hospitalization status to determine CRT Responder Assessment classification
2. Perform device interrogation:
 - Determine LV lead impedance
 - Determine LV lead R-wave sensing amplitude
 - Determine the LV pacing threshold at 0.4 ms pulse width for the programmed pacing vector

Determine LV pacing threshold @ any pulse width (allowing for a minimum 2.5 V safety margin) and document occurrence of phrenic nerve stimulation for additional LV pacing vectors.

3. Screen subject for MPP sub-study by confirming subject meets all of the MPP sub-study specific inclusion criteria and none of the MPP sub-study specific exclusion criteria (Sections 3.1.3 and 3.1.4). If the subject qualifies for the MPP sub-study, complete MPP sub-study enrollment procedures in Section 3.3.5

3.3.8.2 Adverse event related interim follow-up

For interim follow-ups related to an adverse event, the data collected on the Interim Follow-up eCRF is the same as the 6 and 12 month evaluations (Section 3.3.4).

3.3.8.3 System Revision

For interim evaluations that involve a system revision (even if the Sentus QP lead is not directly affected), the following data is required:

1. Implantation procedure information (date of intervention, information about new implanted devices).
2. Revised device (manufacturer, model, serial number).
3. Sentus QP lead measurements during procedure:
 - Determine LV lead impedance
 - Determine LV lead R-wave sensing amplitudes
 - Determine LV pacing threshold at 0.4 ms pulse width for the pacing vector programmed at the end of intervention.
4. Device programming and settings at end of intervention.

5. Store the electronic procedure data (including final device settings, measurements, episodes) of the BIOTRONIK programmer on an appropriate USB flash drive.
6. Complete the electronic System Revision eCRF.
7. Document any reportable adverse event (e.g. phrenic nerve stimulation, high LV pacing threshold, etc.) during the procedure by using the respective eCRF.

Please note:

1. If prior to MPP sub-study enrollment, the BIOTRONIK Ilivia 7 HF-T QP family CRT-D system or Acticor/Rivacor HF-T QP family CRT-D and/or Sentus QP LV lead were explanted and not replaced with an MPP sub-study eligible system, the subject will be exited from the clinical investigation using a Study Termination eCRF.
2. Whenever possible, BIOTRONIK devices that are explanted must be returned to BIOTRONIK, Inc. for analysis.

3.3.9 Study Termination

A QP ExCELS Study Termination eCRF should only be completed for early study termination. Reasons for early study termination are described in Section 3.4.2. A QP ExCELS Study Termination eCRF is not required for subjects who complete the 6 month QP ExCELS visit and who are not enrolled into the MPP sub-study. For subjects enrolled into the MPP sub-study, an MPP sub-study specific termination eCRF is required to record a study exit; however a QP ExCELS Study Termination eCRF is not required.

3.4 Study Participation Expectations

3.4.1 Point of Enrollment

Subjects are 'provisionally enrolled' into the MPP sub-study upon signing the Informed Consent Form and meeting the inclusion/exclusion criteria at time of consent.

3.4.2 Reasons for Study Termination

Once a subject is enrolled and successfully implanted, every effort should be made to continue to follow the subject in the clinical investigation. However, it is inevitable that some subjects will decline to participate further, change geographic location, or become non-compliant with the visit schedule.

3.4.2.1 No implant attempt

If BIOTRONIK Ilivia 7 HF-T QP family CRT-D system or Acticor/Rivacor HF-T QP family CRT-D system and/or Sentus QP LV lead was not implanted, the subject is exited. The reason for study termination must be provided.

3.4.2.2 Withdrawal of subject consent

Subjects may withdraw their consent for study participation at any time without stating the reason and without any unfavorable consequences. All data, which are collected until the date of withdrawal will be used for analysis. A Study Termination eCRF has to be completed by the investigator in which the reasons for withdrawal should be documented if willingly provided by the subject.

